## • Secondary objective

To assess whether there is a drug-drug interaction with concomitant use of spironolactone.

To measure renal clearance (CLR)/Percent Recovered and unchanged drug excreted in urine (fe)/ Amount Recovered for digoxin in the presence and absence of spironolactone (perpetrator) in healthy adult human subjects under fasting condition.

To monitor safety of the subjects in drug-drug interaction study.

Space left blank intentionally.

Confidential

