## 9.7 STATISTICAL METHODS PLANNED IN THE PROTOCOL AND DETERMINATION OF SAMPLE SIZE

#### 9.7.1 Statistical and Analytical Plans

#### 9.7.1.1 Pharmacokinetic Analysis

Pharmacokinetic parameters for digoxin was calculated from the plasma concentration data and urine data were obtained from all the subjects who completed both the periods, using standard, non-compartmental methods with WinNonlin® Software (version 8.1, Pharsight Corporation, USA). The definition and method of determination for each pharmacokinetic variable is summarized as follows:

Confidential

Primary Pharmacokinetic parame	ters in plasma
C max	Maximum measured plasma concentration.
AUC 0-96	Area under the plasma concentration versus time curve from time 0 to the 96 hour time point concentration.
Secondary Pharmacokinetic parar	neters
T max	Time to achieve maximum plasma concentration. If the maximum value occurs at more than one time point, $T_{max}$ is defined as the first time point with this value.

Pharmacokinetic parameters in urine

CLr	Renal clearance Ae0-240h/AUC0-240 h
fe	Unchanged drug excreted in urine

Concentration-time data that were below limit of quantification were treated as zero for calculations and summary statistics.

Pharmacokinetic analyses included data from samples of subjects who completed both periods of the study.

Descriptive statistics for concentration data were presented for scheduled (nominal) sampling times. Actual elapsed times were used for all pharmacokinetic and statistical analyses only if the samples were withdrawn outside of the permitted window period.

Samples lost / not received from the clinical site, samples processing or arising due to drop out or withdrawal of subjects were to be denoted by the character "M" and excluded from pharmacokinetic analysis.

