## Table 12 Summary Statistics for Untransformed Urine PK Parameters of digoxin Per Treatment

Treatment	Statistics	Renal clearance (CLR)/Percent Recovered	unchanged drug excreted in urine (fe)/ Amount Recovered
	N	28	28
	Mean	54.687	136717.72
I A	SD	29.158	72895.492
Treatment	Min	22.180	55449.800
atm	Median	46.111	115277.98
Tre	Max	147.642	369104.30
	G. Mean	49.042	122606.02
	G.mean %CV	48.257	48.257

Treatment	Statistics	Renal clearance (CLR)/Percent Recovered	unchanged drug excreted in urine (fe)/ Amount Recovered
	N	28	28
	Mean	53.378	133446.07
B	SD	21.256	53141.044
Jeni	Min	21.641	54103.200
Ireatment	Median	51.185	127962.08
Tre	Max	95.602	239003.90
	G. Mean	49.410	123523.87
	G.mean %CV	42.201	42.201

Treatment A: LANOXIN® (digoxin) USP 250 mcg (substrate drug)

Treatment B: LANOXIN® (digoxin) USP 250 mcg + Spironolactone Oral Suspension 100 mg (Carospir® Oral Suspension 20 mL of 25 mg / 5 mL)

The Renal clearance (CLR)/Percent Recovered and unchanged drug excreted in urine (fe)/ Amount Recovered of digoxin was comparable for the Treatment A and Treatment B. The geometric mean Renal clearance (CLR)/Percent Recovered was 49.042 and 49.410 for Treatment A and Treatment B respectively. The geometric mean unchanged drug excreted in urine (fe)/ Amount Recovered was 122606.02 and 123523.87 for Treatment A and Treatment B respectively.

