## 11.4.7 Pharmacokinetic Conclusions

The % Treatment A / Treatment B ratio of digoxin was 64.597% and 84.224% for  $C_{max}$  and AUC0.96 respectively. The lower and the upper limits at 90% confidence interval were 54.18% - 77.02% and 77.45% - 91.59% for  $C_{max}$  and AUC0.96 respectively, which is not within the standard equivalence limit of 80.00-125.00%. Based on the above results presence of drug-drug interaction is established between digoxin and spironolactone.

By comparing  $C_{max}$  and  $AUC_{0.96}$  plasma values of Treatment A and Treatment B, we conclude that these values were increased by 35% and 16% respectively for Treatment B

The Renal clearance (CLR)/Percent Recovered and unchanged drug excreted in urine (fe)/ Amount Recovered of digoxin was comparable for the Treatment A and Treatment B. The geometric mean Renal clearance (CLR)/Percent Recovered was 49.042 and 49.410 for Treatment A and Treatment B respectively. The geometric mean unchanged drug excreted in urine (fe)/ Amount Recovered was 122606.02 and 123523.87 for Treatment A and Treatment B respectively.

Protocol No. C-CMP-SPI-001

Confidential

(Fasting Condition)

Confidential

By comparing these values, we conclude that there is not much difference between Treatment A and Treatment B, with respect to Renal clearance (CLR)/Percent Recovered and unchanged drug excreted in urine (fe)/ Amount Recovered.

Confidential

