### Use in Patients with Electrolyte Disorders

In patients with hypokalemia or hypomagnesemia, toxicity may occur despite serum digoxin concentrations below 2.0 ng/mL, because potassium or magnesium depletion sensitizes the myocardium to digoxin. Therefore, it is desirable to maintain normal serum potassium and magnesium concentrations in patients being treated with digoxin. Deficiencies of these electrolytes may result from malnutrition, diarrhea, or prolonged vomiting, as well as the use of the following drugs or procedures: diuretics, amphotericin B, corticosteroids, antacids, dialysis, and mechanical suction of gastrointestinal secretions.

Hypercalcemia from any cause predisposes the patient to digitalis toxicity. Calcium, particularly when administered rapidly by the intravenous route, may produce serious arrhythmias in digitalized patients. On the other hand, hypocalcemia can nullify the effects of digoxin in humans; thus, digoxin may be ineffective until serum calcium is restored to normal. These interactions are related to the fact that digoxin affects contractility and excitability of the heart in a manner similar to that of calcium.

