### 6.3 Sampling Schedule

Urine & Blood samples collection will be started after the completion of dosing on Day 6.

A total of 11 urine samples will be collected from each subject in each study period.

Urine samples will be collected at intervals of (0.00-1.00), (1.00-2.00), (2.00-4.00), (4.00-6.00), (6.00-8.00), (8.00-12.00), (12.00-16.00), (16.00-24.00), (24.00-48.00), (48.00-72.00) and (72.00-96.00) hours post dose.

Immediately out of the total volume of urine collected at each collection time interval, approximately 10 mL (2 x 5 mL aliquots) of urine samples will be transferred into two pre-labeled containers for analysis. They will be stored at deep freezer maintained at  $-20^{\circ}$ C or lower until dispatched from Clinical Unit to Bioanalytical Department for analysis.

A total of  $25(1 \times 5 \text{ mL})$  blood samples will be collected from each subject in each study period. Blood samples will be collected at pre-dose (0.00) and post dose at 0.25, 0.50, 0.75, 1.00, 1.33, 1.67, 2.00, 2.33, 2.67, 3.00, 3.50, 4.00, 5.00, 6.00, 8.00, 10.00, 12.00, 16.00, 24.00, 36.00, 48.00, 60.00, 72.00 and 96.00 hours post dose in each period.

Note: Blood samples up to 3 hours post dose will be collected at bed side.

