#### 9 PHARMACOKINETIC ASSESSMENTS

Concentration data of subjects versus time, which are received after analysis of samples, will be included in the final data analysis. Data from subjects with

VASAVIINSTITUTIONAL ETHIGEGINNITEEMP-S APPROVED

Protocol for Drug-Drug Interaction Study of Spironolactone and Digoxin (Fasting Condition) Confidential

missing concentration values (missed blood samples, lost samples, samples unable to be quantified) may be used if pharmacokinetic parameters can be estimated using remaining data points, otherwise data from these subjects will be excluded from the final analysis.

All concentration values below the limit of quantification (BLQ) will be set to zero for all pharmacokinetic and statistical calculations. Any missing samples will be reported as 'Missing' and will be denoted as "M" while running pharmacokinetic and statistical analysis.

The following pharmacokinetic parameters will be computed using noncompartmental model of Phoenix WinNonlin Professional Software Version 6.4 (Pharsight Corporation, USA) or above.

Pharmacokinetic Parameters for digoxin in plasma:

Primary Pharmacokinetic parameters

C max	:	Maximum measured plasma concentration.						
		Area under the plasma concentration versus time curve						
AUC 0-96	:	from time 0 to the 96 hour time point concentration,						
		calculated by linear trapezoidal method.						

Secondary Pharmacokinetic parameters

Time to achieve maximum plasma concentration. If the
 Tmax : maximum value occurs at more than one time point, Tmax is defined as the first time point with this value.

Pharmacokinetic Parameters for digoxin in urine:

CLR: Renal clearance Ae0-240h/AUC0-240h

fc: Unchanged drug excreted in urine

For all the above computations, actual time points of the sample collection will be used in case of sample collection deviations.

In clinical phase or sample analysis process, if 3 or more consecutive post dose samples for any subject are found to be missing, samples of such subjects will be analyzed but pharmacokinetic data of those subjects will be excluded from the final statistical analysis.

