Statistical Analysis Plan: February 2018

An open label, balanced, randomized, single-dose, two-treatment, two-sequence, twoperiod, crossover oral drug-drug interaction study of spironolactone (perpetrator) and Digoxin (substrate drug) in healthy adult human subjects under fasting condition.

PHARMACOKINETIC ASSESSMENTS:

Concentration data of subjects versus time, which are received after analysis of samples, will be included in the final data analysis. Data from subjects with missing concentration values (missed blood samples, lost samples, samples unable to be quantified) may be used if pharmacokinetic parameters can be estimated using remaining data points, otherwise data from these subjects will be excluded from the final analysis.

All concentration values below the limit of quantification (BLQ) will be set to zero for all pharmacokinetic and statistical calculations. Any missing samples will be reported as 'Missing' and will be denoted as "M" while running pharmacokinetic and statistical analysis.

The following pharmacokinetic parameters will be computed using noncompartmental model of Phoenix WinNonlin Professional Software Version 6.4 (Pharsight Corporation, USA) or above.

Pharmacokinetic Parameters for digoxin in plasma:

Primary Pharmacokinetic parameters

Cmax : Maximum measured plasma concentration.

AUC0-96 : Area under the plasma concentration versus time curve from time 0 to the 96 hour time point concentration, calculated by linear trapezoidal method.

Secondary Pharmacokinetic parameters

Tmax : Time to achieve maximum plasma concentration. If the maximum value occurs at more than one time point, Tmax is defined as the first time point with this value.

Pharmacokinetic Parameters for digoxin in urine:

CLR: Renal clearance Ae0-240h/AUC0-240 h

fe: Unchanged drug excreted in urine

For all the above computations, actual time points of the sample collection will be used in case of sample collection deviations.

In clinical phase or sample analysis process, if 3 or more consecutive post dose samples for any subject are found to be missing, samples of such subjects will be analyzed but pharmacokinetic data of those subjects will be excluded from the final statistical analysis.

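### Renal clearance is defined over 0-240 h although sampling stops at 96 h, and the summarised clearance column is percent of dose, so no clearance shown supports the comparability statement

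*SAP*

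**What the plan says.** The SAP gives "CLR: Renal clearance Ae0-240h/AUC0-240 h". Protocol Section 9 has "CL R : Renal clearance Ae 0-240h /AUC 0-240h", and Section 9.7.1.1 of the study report still has "Renal clearance Ae0-240h/AUC0-240 h". Protocol Section 6.3 ends urine collection with the intervals "48.00-72.00) and (72.00-96.00) hours post dose" and takes the last plasma sample at 96 h. The only AUC planned is AUC0-96, and neither document provides for extrapolation beyond it.

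The urine measures serve a secondary objective: "To measure renal clearance (CLR)/Percent Recovered and unchanged drug excreted in urine (fe)/ Amount Recovered for digoxin". The SAP and Protocol Section 10.7 treat them as supportive, with no model, interval or criterion.

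Below Table 12 the report states: "The geometric mean Renal clearance (CLR)/Percent Recovered was 49.042 and 49.410 for Treatment A and Treatment B respectively". Section 11.4.7 repeats these values and the amounts recovered, and from them concludes: "we conclude that there is not much difference between Treatment A and Treatment B, with respect to Renal clearance (CLR)/Percent Recovered".

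**The concern.** Three things do not fit together: a 240 h definition, 96 h of data, and a summary column whose values look like percentages. Renal clearance is amount excreted divided by plasma AUC. If the same amount is excreted while plasma exposure is higher, clearance is lower. Equal recovery therefore says nothing about equal clearance unless AUC is also equal, and in this study it is not.

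What is at stake is a stated secondary objective and the explanation of the interaction. A reader of Section 11.4.7 would take it that renal elimination of digoxin is unchanged by spironolactone, although no clearance summary is shown. Two further points bear on the same parameter: one recovery exceeds the dose, and the plasma unit needed to compute a clearance is in doubt.

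**Working it through.** **Inputs.** Dose 250 mcg = 250,000 ng in both treatments (Protocol Section 6.1). Urine summaries are from Table 12, geometric mean AUC0-96 from Table 10, and the AUC intra-subject CV of 18.56% from Table 11. n = 28, all with both periods. Digoxin half-life is 1.5-2.0 days (Protocol Section 2.2.3).

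**Step 1: the time window.** At a half-life of 36-48 h, 96 h is 96/48 = 2.0 to 96/36 = 2.7 half-lives, and 240 h is 5.0 to 6.7. The 0-240 h quantities cannot be read from 0-96 h data without extrapolation, and none is planned.

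**Step 2: reproducing the reported column.** Percent of dose = 100 × amount / 250,000 = amount / 2500.

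| Statistic | A: amount | A: /2500 | A: reported | B: amount | B: /2500 | B: reported |
|---|---|---|---|---|---|---|
| Mean | 136717.72 | 54.687 | 54.687 | 133446.07 | 53.378 | 53.378 |
| SD | 72895.492 | 29.158 | 29.158 | 53141.044 | 21.256 | 21.256 |
| Minimum | 55449.800 | 22.180 | 22.180 | 54103.200 | 21.641 | 21.641 |
| Median | 115277.98 | 46.111 | 46.111 | 127962.08 | 51.185 | 51.185 |
| Maximum | 369104.30 | 147.642 | 147.642 | 239003.90 | 95.602 | 95.602 |
| Geometric mean | 122606.02 | 49.042 | 49.042 | 123523.87 | 49.410 | 49.410 |

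All 12 entries agree to three decimals. The geometric CVs of the two columns are also identical (48.257 and 48.257 in A; 42.201 and 42.201 in B), as they must be when one column is the other divided by a constant. The match also implies that the amounts, printed without a unit, are in ng.

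**Step 3: what the report's own figures imply for clearance.** The same 28 subjects enter both means, so the geometric mean of Ae/AUC equals the ratio of the geometric means.

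- A: 122606.02 / 13473.043 = 9.100
- B: 123523.87 / 15996.644 = 7.722
- Amount B/A = 1.007; AUC0-96 B/A = 1.187; clearance B/A = 7.722 / 9.100 = 0.849

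**Step 4: precision.** The within-subject variability of clearance is not reported, so an interval needs assumptions. With s² = ln(1 + CV²), ln Ae has variance 0.2093 in A and 0.1639 in B.

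- var(difference in ln Ae) = sA² + sB² − 2·rho·sA·sB, where rho is the between-period correlation
- var(difference in ln AUC) = 2·ln(1 + 0.1856²) = 0.0677
- SE = sqrt(sum / 28), with t(26) = 1.7056

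As a check, the AUC term alone gives 77.45-91.59% around 84.224%, which is the reported interval. Assuming that the Ae and AUC differences are uncorrelated:

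| rho for Ae | 90% CI for clearance B/A |
|---|---|
| 0 | 0.69-1.05 |
| 0.5 | 0.72-1.00 |
| 0.7 | 0.74-0.97 |
| 0.9 | 0.76-0.94 |

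The result is sensitive to that second assumption. With a correlation of −0.5 between the two differences, the upper limit becomes 1.03 at rho 0.5 and 1.003 at rho 0.7. With +0.5, the upper limit at rho 0 is 1.007.

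**Step 5: the recovery above dose.** 369104.30 / 250000 = 1.476, so one Treatment A profile shows 147.6% of a single dose. For scale, the protocol's typical ranges for absorption (60-80%) and urinary excretion (50-70%) give 0.60 × 0.50 = 30% to 0.80 × 0.70 = 56%; these are typical values, not limits for one subject. Replacing that one value, for illustration only:

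- by 100% of dose: 0.8485 × (147.642/100)^(1/28) = 0.860
- by the A geometric mean: 0.8485 × (147.642/49.042)^(1/28) = 0.883

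**Step 6: units.** As labelled (ng and ng·hr/mL), clearance in A is 9.100 mL/h, or 0.152 mL/min. If the plasma values were in pg/mL (an assumption), it would be 9.100 L/h, or 152 mL/min. Geometric mean Cmax is tabulated as 1456 and 2254 ng/mL, while the protocol warns that in patients with low potassium or magnesium "toxicity may occur despite serum digoxin concentrations below 2.0 ng/mL". The unit cancels from B/A but not from any absolute clearance.

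**The case against.** The strongest reply is that nothing was concealed. The objectives use the compound label of renal clearance and percent recovered, so percent recovered may have been an accepted form of a supportive measure. The 240 h window looks like an uncorrected entry, since everything else in the plan points to 96 h. The individual urine tables are not in the text available here, so a per-subject clearance could exist in them. It is fair that the label is disclosed and the intended window easy to guess. But a compound label does not turn recovery into clearance, and Section 11.4.7 draws its conclusion by comparing the summary values themselves, not an unshown clearance.

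The objection to the size has more force. The 0.849 ratio is built on urine amounts that include an impossible value, and the number of other affected profiles is unknown. Limiting the 30-56% benchmark to 96 h by simple first-order elimination (an assumption) gives 0.30 × 0.75 = 22% to 0.56 × 0.84 = 47%. Both geometric means, 49.0 and 49.4, lie above that, which raises a question about absolute recovery in both treatments. Whether the interval excludes 1 is settled by the assumed correlations. So 0.849 is no evidence of a proven fall; it shows only that equal clearance does not follow from the reported data.

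It is also true that a formal model for a supportive parameter is a choice, and that dropping recoveries above 100% would remove Treatment A values only (the B maximum is 95.6%) and push B/A upward. Source verification should therefore come before any exclusion.

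**Conclusion.** The concern holds. The clearance definition cannot be executed with the sampling schedule, and the summarised column is percent of dose recovered. The comparability statement is supported for percent and amount recovered (B/A 1.007) and unsupported for renal clearance.

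The report's own figures give a provisional clearance ratio B/A of 0.849, or 0.860 to 0.883 when the one impossible value is replaced as illustrated. Under the assumptions shown, the 90% CI runs from 0.69-1.05 to 0.76-0.94, and wider if the Ae and AUC differences are negatively correlated. A fall in clearance is neither shown nor excluded.

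This should be fixed because a secondary objective rests on it. The urine data are supportive, and the interaction conclusion from Cmax and AUC0-96 does not change.

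**What to change.** - In the SAP, Protocol Section 9 and report Section 9.7.1.1, define renal clearance as Ae0-96/AUC0-96 with stated units, after reconciling the plasma concentration unit.
- Report renal clearance and percent of dose recovered as two separate parameters, each with its unit, and give the amount recovered in ng.
- Compute clearance per subject and period, analyse ln(CLR) with the existing crossover model, and give the B/A ratio with 90% CI as supportive data, without an equivalence margin.
- Check concentration × volume × dilution at source for every recovery above 100% of dose. Then show results with and without any such profiles that remain.
- Withdraw the comparability statement on renal clearance until this is done, and keep it for percent and amount recovered.

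The cost is one corrected definition, one extra ANOVA on data already collected, and a source check of urine volumes, dilutions and the plasma unit. As the report is already dated, the change to it would be a correction.
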